Aim 2. To assess the effectiveness of the MBST intervention at increasing mindfulness skills. As a manipulation check, we investigated whether the MBST intervention improved mindfulness skills. We hypothesized that participants in the MBST intervention would increase mindfulness skills from baseline (before the intervention) to follow-up (after the intervention). Specifically, we hypothesized that participants in the MBST intervention would increase their ability to observe, describe, accept without judgment, and act with awareness.

Aim 3. To assess the effectiveness of the MBST intervention at improving emotion regulation. As a manipulation check, we investigated whether the MBST intervention improved emotion regulation. We hypothesized that participants in the MBST intervention will improve emotion regulation skills from baseline (before the intervention) to follow-up (after the intervention). Specifically, we hypothesized that participants in the MBST intervention would improve their emotional awareness, emotional clarity, acceptance of emotional responses, impulse control, access to emotion regulation strategies, and ability to engage in goal-directed behavior.

Aim 4. To evaluate the effectiveness of the MBST intervention (treatment) and psychoeducational intervention (active control) at reducing the perpetration of dating violence (physical, sexual, and psychological).

Aim 4a. To assess the effectiveness of the psychoeducational intervention at reducing the perpetration of dating violence. Before comparing the effectiveness of the interventions against one another, we first planned to assess each intervention

individually. We hypothesized that the psychoeducational intervention would reduce dating violence perpetration (physical, psychological, and sexual) from baseline (before the intervention) to follow-up (after the intervention); however, given the evidence that psychoeducational interventions are largely ineffective we did not expect the reduction to be statistically significant.

Aim 4b. To assess the effectiveness of the MBST intervention at reducing the perpetration of dating violence. We hypothesized that the MBST intervention would significantly reduce dating violence perpetration (physical, sexual, and psychological) from baseline (before the intervention) to follow-up (after the intervention).

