Participants were recruited to complete a baseline assessment, an intervention portion (consisting of three 50-minute sessions with homework in-between sessions), a seven-day daily diary, and a follow-up assessment. All participants completed the initial baseline assessment the fourth week of classes. During this assessment, data was collected on demographics, dating

violence (during the past month), emotion regulation, mindfulness skills, attitudes condoning dating violence, and other potential covariates (relationship length, relationship satisfaction, externalizing behavior problems, anxiety, depression, substance use, use of mindfulness practices in the past month, social desirability).

Following this baseline assessment, participants were randomized into either (1) the MBST intervention or (2) the psychoeducational intervention. Each intervention consisted of three 50-minute sessions that occurred during the sixth, seventh, and eighth week of the semester. In-between sessions all participants were asked to complete homework. Homework assignments were turned in the following week, with the final homework assignment being completed online as part of the first daily diary (since participants did not meet physically the week following the final session). There were two semesters of data collection total. All intervention sessions occurred at the same time (6:00 – 6:50 PM) on Tuesday nights. Conditions were counter balanced with graduate students leading the sessions, social support of groups, and homework. We attempted to counter balance based on room location, but the availability of rooms changed between semesters. However, no treatment condition was given in the same room twice and rooms were selected to be as similar as possible (number of desks, void of windows, etc.).

The week following the final intervention session, participants completed a seven-day daily diary assessment. During this assessment, participants in the MBST intervention were asked to report whether they had used any of the skills learned in the intervention (see below for detailed information on skills), and to describe what happened when they used the skill(s) (who they were with, if it helped, etc.). To balance the conditions, participants in the psychoeducation intervention were asked to indicate whether they had seen any examples of dating abuse in the

media that day. If they had, they were asked to describe who the victim, target, and bystanders were in each example.

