Eleven weeks after the baseline assessment, all participants completed the follow-up assessment. During this assessment, participants completed another battery of assessments. Self-reported data was collected on dating violence (during the last month), attitudes condoning dating violence, emotion regulation, and mindfulness skills. The entire protocol carefully followed the CONSORT statement guidelines.

Interventions

Mindfulness-Based Skills Training (MBST) intervention. Some traditional mindfulness-based interventions teach mindfulness through the practice of meditation. However, the goal of this intervention was to teach students how to be mindful in a specific situation: when resolving conflict with their romantic partners. Thus, this intervention took a more “mindfulness applied” approach. The previously mentioned skills of observing one’s own internal experiences and sensations, accepting one’s own internal experience without judgment, being able to describe one’s experience by putting it into words, and acting with awareness were still the basis for this intervention. However, these skills were taught in a “user-friendly” format that is specific to the context of resolving conflict with one’s romantic partner. This format helped students learn how to mindfully become aware of when they were experiencing emotionally charged states, how to calm themselves down through mindful breathing, to put their experience into words, and to act with awareness as they communicated with their partners in a healthy and mindful way. The skills followed the “ABCDE” acronym. ABCDE stands for **a**wareness, **b**reathing, **c**hecking in with your feelings and thoughts, **d**escribing your experience, and **e**xpressing what you want to change. A variety of skills taught in the ABCDE intervention (paced breathing, observing

feelings, observing thoughts, decentering) are used in a variety of other skills trainings such as Dialectical Behavioral Therapy and Acceptance and Commitment Therapy (Linehan, 2014; Luoma, Hayes, & Walser, 2007). An advanced PhD student led the sessions, but the curriculum is designed so that anyone (teacher, staff member, etc.) can deliver it. Below is a brief description of what was included in each session (see appendices for detailed training manual).

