Preliminary analyses. We first conducted bivariate analyses to investigate whether participants who dropped out of the study differed from those who remained in the study on key characteristics. To do this, we created a variable that indicated whether a participant had dropped out of the study and used that variable to investigate associations with age, ethnicity, relationship length, relationship satisfaction, externalizing behavior problems, anxiety, depression, substance use, attitudes condoning dating violence, use of mindfulness, and social desirability at baseline. If the drop out variable was associated with any of the potential covariates, we included the covariate(s) in all subsequent analyses.

We then investigated the associations between potential covariates and each individual outcome. If a potential covariate was significantly associated with an outcome ($p < .05$), we included it in subsequent analyses. For example, we first investigated whether “attitudes condoning dating violence” at follow-up (IPVAS – R, Aim 1 outcome) was associated with age, ethnicity, relationship length, relationship satisfaction, externalizing behavior problems, anxiety,

depression, substance use, attitudes toward dating violence, use of mindfulness, and social desirability at baseline. If “attitudes condoning dating violence” was associated with any of the covariates, we controlled for them in my Aim 1 analyses. We then repeated for the rest of the aims (Aim 2; each subscale of mindfulness skills, Aim 3; each subscale of emotion regulation; Aim 4; dating violence)³.

Furthermore, we investigated differences between treatment groups based on age, gender, attitudes, mindfulness skills, emotion regulation, and levels of dating violence perpetration at baseline for descriptive purposes.

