Aim 1. To assess whether participants in the psychoeducational intervention improved their attitudes condoning dating violence [IPVAS – R] (a manipulation check), we examined mean differences using a paired t-test with covariates in Mplus (Muthén & Muthén, 2007). This technique also allows us to use the FIML estimator within Mplus and to intercorrelate covariates (e.g., anxiety and depression). Please note this analysis only included participants who were assigned to the psychoeducational intervention (and did not include those in the MBST intervention). Please note that a *decrease* in means indicates improvement, as higher scores on the IPVAS – R indicate attitudes that *condone* dating violence.

Aim 2. To assess whether participants in the MBST intervention improved their mindfulness skills (a manipulation check), we examined mean differences paired t-test with covariates. These tests compared the means of mindfulness skills at baseline to the mean of mindfulness skills at follow-up, controlling for covariates identified in preliminary analyses. Please note this analysis only included participants who were assigned to the MBST intervention

³ One potential concern with this analysis plan is that covariates depend on the outcome of interest, so differences in results may be due to differences in covariates included. To address this, we ran analyses with and without the unique covariates; findings remained the same.

(and did not include those in the psychoeducational intervention). Tests were run individually for all four subscales [observing (KIMS – OB), describing (KIMS – DE), acting with awareness (KIMS – AW), acceptance without judgement (KIMS – AC)].

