Aim 3. To assess whether participants in the MBST intervention improved their emotion regulation (a manipulation check), we examined mean differences using paired t-tests with covariates. These tests compared the means of emotion regulation subscales at baseline to the mean of emotion regulation subscales at follow-up, controlling for covariates identified in preliminary analyses. Please note this analysis only included participants who were assigned to the MBST intervention (and did not include those in the psychoeducational intervention). Tests were run individually for all six subscales (lack of emotional awareness [DER – EA], lack of emotional clarity [DER – EC], nonacceptance of emotional responses [DER – NE], impulse control difficulties [DER – IC], limited access to emotion regulation strategies [DER – ER], and difficulties engaging in goal-directed behavior [DER – DE]). Please note that a *decrease* in means indicates improvement, as higher scores on the Difficulties in Emotion Regulation Scale indicate more problems with emotion regulation.

Aim 4a. To assess whether participants in the psychoeducational intervention reduced dating violence perpetration from baseline (before the intervention) to follow-up (after the intervention) we examined paired t-tests with covariates. These tests compared the mean of dating violence perpetration at baseline to the mean of dating violence perpetration at follow-up, controlling for covariates identified in preliminary analyses. Please note this analysis only included participants who were assigned to the psychoeducational intervention (and did not include those in the MBST intervention). Please also note analyses were run separately for each type of dating violence (physical, sexual, psychological).

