Aim 4b. To assess whether participants in the MBST intervention reduced psychological dating violence perpetration from baseline (before the intervention) to follow-up (after the intervention) we examined mean differences using paired t-tests with covariates. These tests compared the mean of dating violence perpetration at baseline to the mean of dating violence perpetration at follow-up, controlling for covariates identified in preliminary analyses. Please note this analysis only included participants who were assigned to the MBST intervention (and did not include those in the psychoeducational intervention). Please also note analyses were run separately for each type of dating violence (physical, sexual, psychological).

Aim 4c. We used a regression framework to investigate the effectiveness of the MBST intervention at reducing dating violence perpetration as compared to the psychoeducational intervention. We chose to run my analyses within a regression framework in Mplus as this allowed for intercorrelations among predictors (e.g., anxiety and depression were included as covariates so we could account for their intercorrelation) and the use of FIML to handle missing data. We used dummy coding to create a variable to differentiate treatment groups. Within a regression framework, we used this dummy-coded variable to predict our outcome (dating violence). We controlled for baseline levels of dating violence perpetration and included other covariates based on preliminary analyses. This analysis, as compared to the analyses for Aims 1 – 3, included participants from both groups. Please also note analyses were run separately for each type of dating violence (physical, sexual, psychological).

Intent to treat analyses. As guided by the Consolidated Standards of Reporting Trials (CONSORT; Schulz, Altman, & Moher, 2010), the number of participants in each group were analyzed according to the intent-to-treat (ITT) principle. ITT is a collective strategy for design, conduct, and analysis in which all participants who are randomized to a group are treated as if

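### The 11 manipulation-check tests in Aims 1–3 judge effectiveness by before-after change within one arm, so change common to both arms can be credited to the intervention

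*Combined protocol and SAP*

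**What the plan says.** Under Aims and Hypotheses, Aims 1–3 are called manipulation checks but are worded as questions of effectiveness; Aim 2, for example, reads "To assess the effectiveness of the MBST intervention at increasing mindfulness skills". The hypotheses are stated as change from baseline to follow-up.

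The Analysis Plan tests each within one arm:

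- **Aim 1** (IPVAS-R total, psychoeducational arm only): "we examined mean differences using a paired t-test with covariates in Mplus".
- **Aim 2** (four KIMS subscales, MBST arm only): paired t-tests with covariates.
- **Aim 3** (six DERS subscales): the same method, and "this analysis only included participants who were assigned to the MBST intervention (and did not include those in the psychoeducational intervention").

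The comparator data exist. Under Trial design, the baseline battery given to everyone covers "emotion regulation, mindfulness skills, attitudes condoning dating violence, and other potential covariates". For the second battery, which repeats these three scales, the text says "Eleven weeks after the baseline assessment, all participants completed the follow-up assessment".

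The only planned between-arm look at these scales is in Preliminary analyses, which examines "differences between treatment groups based on age, gender, attitudes, mindfulness skills, emotion regulation, and levels of dating violence perpetration at baseline for descriptive purposes". Aim 4c, on dating violence, is the only between-arm outcome analysis. Its text says that, unlike Aims 1–3, it "included participants from both groups".

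**The concern.** A before-after change in one arm is the intervention's effect plus whatever would have happened anyway. Several sources of common change are plausible here. Baseline is in week 4 of the semester and follow-up is 11 weeks later, about week 15. All the scales are repeated self-reports. Both arms receive three sessions, homework and a seven-day diary. Adjusting for baseline covariates does not remove such change; the other randomised arm can, but the plan leaves it out.

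Aims 2 and 3 carry the explanatory weight. The Objectives present emotion regulation, taught through mindfulness, as the route by which MBST should reduce perpetration. If a shift shared by both arms can pass the check, a null in Aim 4c may be read as skills having improved without violence falling. A positive result may be read as violence having fallen because skills improved. Neither reading would be supported by the analysis.

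Aims 4a and 4b have the same one-arm form, but they are a stated preliminary step ("Before comparing the effectiveness of the interventions against one another") and Aim 4c then answers the comparative question with a randomised, baseline-adjusted test. They need only a sentence on interpretation.

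**Working it through.** The plan gives no figure for these tests to reproduce. It says the sample size came from G*Power3 but states no effect size, alpha or power.

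**Inputs from the documents.** 88 participants remain after exclusions and allocation is 1:1 (Participants; Trial design). Number of tests: 1 IPVAS-R + 4 KIMS + 6 DERS = 11.

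**Assumptions.** 44 per arm (88/2; arm sizes are not stated), or 30 completers per arm to allow for dropout. Two-sided alpha 0.05 (the plan gives p < .05 only for covariate selection). Baseline/follow-up correlation r of 0.5 or 0.7. A plain paired t-test stands in for the covariate-adjusted FIML version. The size and direction of any common drift are not in the documents.

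**Step 1: one within-arm check with no intervention-specific effect.** Let d be the common drift in SDs of the change score. The paired t statistic is noncentral t with n − 1 degrees of freedom and noncentrality d√n. At n = 44 and d = 0.3 the noncentrality is 0.3 × √44 = 1.99, against a critical value of 2.017.

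| Common drift d | n = 44 | n = 30 |
|---|---|---|
| 0 | 5.0% | 5.0% |
| 0.1 | 9.9% | 8.3% |
| 0.2 | 25.4% | 18.5% |
| 0.3 | 49.4% | 35.5% |
| 0.4 | 73.7% | 56.3% |

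These are two-sided rates. With no drift, half of the 5% (2.5%) is in the favourable direction. From d = 0.2 upwards almost all of it is in the direction of the drift.

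**Step 2: a between-arm contrast under the same drifts.** Follow-up score is regressed on arm and baseline score. In simulation (20,000 trials per setting, 44 per arm, d from 0.1 to 0.4, r = 0.5 and 0.7) the arm coefficient was significant 4.7% to 5.4% of the time. The common drift cancels.

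**Step 3: what the contrast costs.** In baseline-SD units, the standard error of the one-arm change is √(2(1 − r)/n) and that of the baseline-adjusted contrast is √(2(1 − r²)/n). Their ratio is √(1 + r):

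- r = 0.5: √1.5 = 1.225, or 22% larger.
- r = 0.7: √1.7 = 1.304, or 30% larger.

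Power for an assumed true effect of 0.3 baseline SD, with no drift:

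| n per arm | r | Within-arm | Between-arm |
|---|---|---|---|
| 44 | 0.5 | 49% | 36% |
| 44 | 0.7 | 71% | 50% |
| 30 | 0.5 | 36% | 26% |
| 30 | 0.7 | 54% | 36% |

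Steps 1 and 3 use different SD units. The change-score SD is √(2(1 − r)) baseline SDs, so the two units coincide at r = 0.5 but not at r = 0.7.

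**The case against.** The strongest reply is that these are manipulation checks whose hypotheses are worded as within-arm change, so the tests match them. No mediation analysis or decision rule depends on Aims 2–3, and the efficacy question is already tested between arms in Aim 4c. This limits the severity. It does not rescue the claim of effectiveness, because a check that shared drift can pass does not show that the intervention moved the skill.

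The size is also illustrative. Drift could run the other way: with an adverse drift of 0.2 SD and 44 per arm, a within-arm check shows false improvement only 0.06% of the time. That is still bias, now hiding a real gain.

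Three criticisms of the remedy have substance:

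- **Power.** It is modest: 36% to 50% at 44 per arm and 26% to 36% at 30. A non-significant arm coefficient would say little.
- **Multiplicity.** Ten decisive tests for Aims 2–3 give a 1 − 0.95¹⁰ = 40% chance of at least one false positive if independent. The planned ten within-arm tests carry the same burden with no multiplicity rule, so this does not favour them.
- **Timing.** The Blinding section relies on analyses fixed in advance and on group codes hidden until they were finished. Models added now fall outside that safeguard. Labelling them discloses this but does not restore the blinding.

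For Aim 1 the contrast is less decisive. The comparator is active and MBST session 1 deliberately shares some psychoeducational content, so a null could mean both arms improved.

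**Conclusion.** The concern holds. All 11 tests in Aims 1–3 are one-arm before-after comparisons under aims worded as effectiveness, and none has a between-arm counterpart at follow-up although the data are collected. A favourable common drift of 0.2 to 0.3 SD of the change score would make a single check significant about 25% to 49% of the time at 44 per arm (19% to 36% at 30) with no intervention-specific effect, against about 5% for the between-arm contrast. These figures rest on the assumed alpha, arm sizes, correlations and drift; they show the exposure and do not estimate bias in this trial. The point should be fixed because it changes what Aims 2 and 3 can conclude. It leaves Aim 4c untouched.

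**What to change.** 1. For the IPVAS-R total, each KIMS subscale and each DERS subscale, add the Aim 4c model: follow-up score on arm indicator and that scale's baseline value, all randomised participants, FIML, and the same covariate rule as Aim 4c. Label these models as added after the original analyses.
2. For Aims 2 and 3, rest any statement that MBST improved mindfulness or emotion regulation on the arm coefficient. Report the within-arm change as an estimate with a 95% confidence interval.
3. For Aim 1, report the between-arm contrast beside the within-arm change and describe it as an effect relative to an active comparator with some shared content.
4. For Aims 4a and 4b, report within-arm changes with confidence intervals. State that conclusions on effectiveness against dating violence rest on Aim 4c, and not on one arm's change being significant while the other's is not.

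The cost is wording plus 11 regressions on data already collected. The between-arm standard errors are larger, so some checks may look less favourable; intervals should be shown and a non-significant coefficient should not be read as no effect. The contrast also does not remove arm-specific demand, because the arms teach different content and the scales are self-reported. The report should say so.

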Aim 4c. To assess the effectiveness of the MBST intervention compared to a psychoeducational intervention (active control) at reducing the perpetration of dating violence. We hypothesized that the MBST intervention will be more effective at reducing dating violence perpetration (physical, sexual, and psychological) as compared to the psychoeducational intervention.

Methods

Participants

100 participants were recruited through Kent State University's online subject pool. Sample size was determined using G*Power3 (Faul, Erdfelder, Lang, & Buchner, 2007). Ninety-one participants completed the initial baseline assessment, and three participants were excluded from the rest of the study for not meeting inclusion criteria (see below; 2 indicated being single, 1 indicated being married). Thus, this study reports on the remaining 88 participants' data.

To be eligible, participants were required to be over the age of 18, in a current dating relationship (of 6 months or longer) and were required to confirm that they had *not* been

diagnosed with psychopathology (Major Depressive Disorder, Post-Traumatic Stress Disorder, Borderline Personality Disorder). At baseline, participants did not differ between assigned treatment groups based on age, ethnicity, gender, depression, anxiety, externalizing behavior problems, or substance use.

Furthermore, only one member of the dating couple could participate in the study. To address issues surrounding contamination, participants were reminded throughout the course of the study that they could not discuss the intervention with anyone (except their romantic partner) until the end of the study.

Data collection was conducted online (except for the first two homework assignments which were handed in using paper copies, used for compliance data; see Data and Safety Monitoring Plan for details surrounding homework collection). Participants were asked to complete online surveys in private, though they could choose where that was (e.g., dorm room or elsewhere). The actual intervention took place on Kent State University's campus, specifically classrooms in Kent Hall (rooms 60, 102, 145, and 167). This study was approved by Kent State University's Institutional Review Board.

Trial design

This study utilized a two-armed, parallel-design. The allocation ratio was 1:1. The treatment group was the MBST intervention and the active control group was the psychoeducational intervention.

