they complied with their assigned treatments (Gupta, 2011). Most likely, not all participants will comply with their assigned treatments and missing data will be an issue. To ensure a conservative estimate of treatment effects (and to avoid confounds of patient characteristics with treatment allocation) ITT analyses were used. We planned to report information on participants who deviated from their random allocation treatment, but no participants deviated into another group. We also reported information on missing data. Specifically, according to CONSORT guidelines we reported “numbers analysed” (number of participants included in each analysis and whether the analysis was by original assigned groups; Schulz, Altman, & Moher, 2010, p. 727).

Missing data. We used full information maximum likelihood (FIML) to handle missing data. FIML is superior to other traditional approaches, such as listwise deletion, as it uses all available information in all observations instead of deleting observations due to missing values (Muthén & Muthén, 2007). Furthermore, as described above, we conducted analyses to investigate if participants who dropped out of the study differed systematically from those who remained in the study. Key characteristics were identified and were controlled for in all analyses.

Randomization. Following baseline data collection, all participants were randomly assigned (see information on blinding below) to either the MBST intervention or the psychoeducational intervention. Randomization represents best practices in research and aims to ensure that each participant is no more likely than the next to be assigned to a particular group. Specifically, we used restricted random allocation to ensure equally-sized groups. To do this the lab coordinator gave the co-PI fake participant IDs for the semester in an excel spreadsheet (e.g., a list of 50 participants with IDs such as 134, 258, 250, 350). The co-PI randomly selected half of the fake participant IDs to be assigned to one group and another half to be assigned to the

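### The plan fits small-sample tests by maximum likelihood without stating a small-sample correction; with model-based standard errors, the nominal 5% Aim 4c test would reject about 5.7% to 7.6% of the time at n = 88

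*Combined protocol and SAP*

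**What the plan says.** Under Aim 4c, the randomised comparison is a regression in Mplus of each dating-violence outcome on a treatment dummy, the baseline level of that outcome and any screened covariates. The reasons given for this framework include "so we could account for their intercorrelation) and the use of FIML to handle missing data".

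For the one-arm analyses, the Aim 1 text says "we examined mean differences using a paired t-test with covariates in Mplus", and adds "This technique also allows us to use the FIML estimator within Mplus and to intercorrelate covariates". Aims 2, 3, 4a and 4b describe paired t-tests with covariates and do not repeat the estimator. The missing-data section is general: "We used full information maximum likelihood (FIML) to handle missing data".

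On sample size, the Participants section says "Thus, this study reports on the remaining 88 participants' data", and the Trial design section says "The allocation ratio was 1:1".

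The preliminary analyses list 11 candidate covariates. One is kept if it is associated with dropout, or with the outcome at p < .05. There is no cap, and the number retained is not given.

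The plan does not mention REML, residual degrees of freedom, a bootstrap, a permutation test or any other small-sample adjustment. It also does not state the type of standard error, the reference distribution, or the alpha and sidedness of the aim tests. The only .05 in the document is the covariate-screening threshold.

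**The concern.** Maximum likelihood estimates the residual variance as SSE/n. Least squares uses SSE/(n - p), where p is the number of regression coefficients, and that divisor is what makes the t-test exact under normality. A model-based ML standard error is therefore too small by the factor sqrt((n - p)/n). If the ratio is then referred to the normal distribution, the critical value is 1.96 instead of the slightly larger t value. Both errors push towards significance.

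In a large trial this is invisible. Here at most 88 people enter Aim 4c and about 44 enter each one-arm test, and the screens may add several covariates. What is at stake is the error rate and interval coverage of the only randomised comparison, which is run separately for physical, sexual and psychological violence. The issue is separate from skewed outcomes and from clustering by session group, because it arises even with normal, independent data.

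**Working it through.** **No stated figure to reproduce.** The plan gives no type I error or power for the aim tests. The recruited 100 is attributed to G*Power3 without inputs, so it cannot be checked.

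**Inputs.**
- m = number with observed follow-up. The documents give only the upper limit, 88 (Participants). A value of 70 is used below as an assumption.
- Aim 4c coefficients: p = 3 + k (intercept, treatment dummy, baseline violence, and k screened covariates). k runs from 0 to 11 (Preliminary analyses), counting one coefficient per covariate.
- One-arm sample: 88/2 = 44, assuming an equal split.
- Assumed because the plan is silent: two-sided 5% test, model-based ML standard errors, normal independent residuals, complete baseline covariates.

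**Formula.** When only the follow-up outcome is missing, the FIML arm effect equals least squares in those followed up. The ML ratio is then the ordinary t statistic multiplied by sqrt(m/(m - p)), which gives:
- true size, normal reference = P(|t(m-p)| > 1.96 × sqrt((m-p)/m))
- true size, t reference = P(|t(m-p)| > t(.975, m-p) × sqrt((m-p)/m))
- interval width relative to the correct one = 1.96 × sqrt((m-p)/m) / t(.975, m-p)

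**Worked ends at m = 88.**
- k = 0: p = 3, df = 85, sqrt(85/88) = 0.983. The effective threshold is 1.96 × 0.983 = 1.926, and P(|t(85)| > 1.926) = 5.7%. Width ratio: 1.926/1.988 = 0.969.
- k = 11: p = 14, df = 74, sqrt(74/88) = 0.917. The effective threshold is 1.797, and P(|t(74)| > 1.797) = 7.6%. Width ratio: 1.797/1.993 = 0.902.

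**Aim 4c results.**

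| m | k | Size, normal reference | Size, t reference |
|---|---|---|---|
| 88 | 0 | 5.7% | 5.4% |
| 88 | 5 | 6.5% | 6.1% |
| 88 | 11 | 7.6% | 7.2% |
| 70 (assumed) | 0 | 5.9% | 5.5% |
| 70 (assumed) | 11 | 8.5% | 7.9% |

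So at m = 88 the intervals are about 3% to 10% too narrow. A result whose exact t-test p-value is 0.050 would be reported as 0.043 (k = 0) to 0.030 (k = 11).

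**Simulation check** (m = 88, 20,000 runs per setting, normal reference). All 11 covariates forced in: 7.6%. With the p < .05 screen and no covariate truly related to outcome: 0.6 kept on average, 5.8%. With the screen and three that matter: 4.7 kept on average, 6.9%. Using SSE/(m - p) with t(m - p), the same three settings gave 4.9%, 5.0% and 5.3%.

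**One-arm tests.** Suppose the change is regressed on k covariates and its adjusted mean is tested, so p = 1 + k. At m = 44 the size is 5.9% (k = 0) to 10.4% (k = 11). If only the marginal mean change is tested, without covariates, simulated FIML gave 5.8% with 44 of 44 followed up and 7.0% with 25 of 44 (baseline to follow-up correlation 0.5, assumed).

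**The case against.** The strongest objection is that FIML names an estimator, not a test. The documents do not say whether standard errors are model-based, robust or bootstrapped, nor which reference distribution is used, and the one-arm procedure is called a t-test. A reader might infer that every p-value in the study is too small and that a nominal 5% test rejects 6% to 8% of the time. The documents do not support that as a flat statement. The rate depends on the standard-error type, on the number followed up and on the number of covariates kept, and none of these is given. At the one documented sample size, 88, the figure with no extra covariates is 5.7%, and even all 11 give only 7.6%. Anything above that requires attrition that the documents do not quantify. The rates are also exact only for normal, independent residuals, and these outcomes are past-month violence scores from interventions delivered in groups.

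This stands, and it makes the finding conditional. It does not remove it. If the standard errors are model-based, the n divisor comes with the estimator, and a t reference alone still leaves 5.4% to 7.2%.

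Footnote 3 reports that conclusions did not change with or without the outcome-specific covariates. That lowers the concern about covariate choice. Both sets of analyses are described under the same estimator, however, so it says nothing about the variance divisor.

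A reader might also infer that a reported Aim 4c conclusion is wrong. Nothing supports this. With a normal reference at n = 88, only results with a correct p-value between 0.05 and about 0.057 (no extra covariates) or 0.076 (all 11) would change side, and the documents show no result in that band.

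**Conclusion.** The concern holds in conditional form. The plan names maximum likelihood for at most 88 people, and about 44 in the one-arm tests, and specifies no small-sample correction. With model-based ML standard errors, a two-sided 5% test, normal independent residuals and complete baseline covariates, the true Aim 4c error at n = 88 is 5.7% to 7.6% with a normal reference, or 5.4% to 7.2% with a t reference. The upper ends need all 11 covariates; with few retained, the rate is nearer 6%. At an assumed 70 followed up, the normal-reference range is 5.9% to 8.5%.

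The size is modest and matters only for borderline results. It still deserves correction, because the bias runs in one direction, reaches the randomised comparison and costs almost nothing to remove.

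**What to change.** **Aim 4c.** Report the arm effect with t-based inference on residual degrees of freedom: multiply the ML standard error by sqrt(m/(m - p)) and refer the ratio to t(m - p), where m is the number with observed follow-up, not the number randomised. When baseline covariates are complete, this is the same as ordinary least squares in those followed up, and the point estimate does not change. If baseline covariates are incomplete, that equivalence fails; use multiple imputation with small-sample degrees of freedom instead.

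**One-arm changes (Aims 1 to 3, 4a, 4b).** Use REML with Kenward-Roger or Satterthwaite degrees of freedom.

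**Text.** State the standard-error type, reference distribution, alpha and sidedness, and report m and p for each model.

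**Cost.** A few sentences and a re-run of existing models, with no new data. At n = 88 intervals widen by about 3% (1/0.969 = 1.03) to 11% (1/0.902 = 1.11), and p-values rise slightly. This does not address skewed outcomes or clustering, which need separate treatment.
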